**Table 12 Toxicity Grading for Selected Laboratory Tests**

Parameter	Unit	Grade 1	Grade 2	Grade 3	Grade 4
Alanine amino transferase (ALT)		>1-3 *ULN	>3-5 *ULN	>5-20 *ULN	>20 *ULN
Alkaline phosphatase (ALP)		>1.0-2.5 *ULN	>2.5-5.0 *ULN	>5.0-20.0 *ULN	>20.0 *ULN
Aspartate amino transferase (AST)		>1-3 *ULN	>3-5 *ULN	>5-20 *ULN	>20 *ULN
Bilirubin (total)		>1.0-1.5 *ULN	>1.5-3.0 *ULN	>3.0-10.0 *ULN	>10.0 *ULN
Creatine kinase		>1.0-2.5 *ULN	>2.5-5.0 *ULN	>5.0-10.0 *ULN	>10.0 *ULN

Paramater	Unit	Grade 1	Grade 2	Grade 3	Grade 4
Creatinine		>1.0-1.5 *ULN	>1.5-3.0 *ULN	>3.0-6.0 *ULN	>6.0 *ULN
Glucose (fasting) low	mmol/L	<LLN-3.0	<3.0-2.2	<2.2-1.7	<1.7
	mg/dL	<LLN-55	<55-40	<40-30	<30
Potassium low	mmol/L	-	<LLN-3.0	<3.0-2.5	<2.5
	mEq/L	-	<LLN-3.0	<3.0-2.5	<2.5
Potassium high	mmol/L	>ULN-5.5	>5.5-6.0	>6.0-7.0	>7.0
	mEq/L	>ULN-5.5	>5.5-6.0	>6.0-7.0	>7.0
Sodium low	mmol/L	<LLN-130	-	<130-120	<120
	mEq/L	<LLN-130	-	<130-120	<120
Sodium high	mmol/L	>ULN-150	>150-155	>155-160	>160
	mEq/L	>ULN-150	>150-155	>155-160	>160
International normalized ratio		>1.2-1.5 *ULN	>1.5-2.5 *ULN	>2.5 *ULN	-
Lymphocytes (absolute count) low	giga/L	<LLN-0.80	<0.80-0.50	<0.50-0.20	<0.20
	counts/mm 	<LLN-800	<800-500	<500-200	<200
Lymphocytes (absolute count) high	giga/L	-	>4-20	>20	-
	counts/mm 	-	>4000-20000	>20000	-
Neutrophils (absolute count) low	giga/L	<LLN-1.5	<1.5-1.0	<1.0-0.5	<0.5
	counts/mm 	<LLN-1500	<1500-1000	<1000-500	<500
Platelets	giga/L	<LLN-75	<75-50	<50-25	<25
	counts/mm 	<LLN-75000	<75000-50000	<50000-25000	<25000
White blood cells	giga/L	<LLN-3	<3-2	<2-1	<1
	counts/mm 	<LLN-3000	<3000-2000	<2000-1000	<1000

If grade is different from grade 1 to 4, grade will be assigned to 0.

For non gradable parameters per NCI CTCAE grading system, shift tables will be created to summarize the number and proportion of participants with shifts from baseline category to post baseline category (“Low”, “Normal”, “High”, treatment-emergent out-of-range) by treatment group and visit. Shift tables from baseline to worst postbaseline category will also be presented. In case of low and high post-baseline values, a category ‘low + high’ will be defined.

For laboratory parameters which can be graded per NCI CTCAE grading system, the information will be summarized using a shift table summarizing the baseline NCI CTCAE grade (0,1,2,3,4) versus post baseline category NCI CTCAE grade by treatment group and visit. Shift tables from baseline to worst post DBTP baseline NCI CTCAE grade will also be displayed. If there is no evaluation, the worst grade will be set to ‘Missing’. Parameters with toxicity grades defined in both directions (decreased and increased) will be shown by direction. Numbers and cumulative numbers over decreasing toxicities grading of participants with treatment-emergent toxicities will also be shown.

All laboratory data will be listed, but only for participants with post baseline abnormalities or toxicity grade  $\geq 1$ .

For ANA titers (SLE panel), the number and percentage of participants will be summarized by category at each visit in SAF set on DBTP. The following categories for ANA titers will be defined:

- Negative, in case of negative result
- Positive:

I	
I	

In case of multiple titers results for the same assessment, the worst assessment (ie most positive) should be considered.

Shift tables from baseline to worst post baseline category (“Negative”, “ Low positive” and “High positive”) will also be presented.

A listing of participants with ANA titer  $> 1:80$  will be provided and will include the following assessments: anti-dsDNA, anti-Smith, anti-phospholipid (anti-cardiolipin IgG and anti-beta-2- glycoprotein IgG), anti-Ro (anti-Ro52 and anti-Ro60), anti-La and anti-U1RNP.

A listing of Laboratory results for participants entering into the SFU period will be provided.

#### 6.4.3 Vital Signs

Vital signs parameters include:

- Temperature (°C)
- Systolic blood pressure (SBP supine position) (mmHg)
- Diastolic blood pressure (DBP supine position) (mmHg)
- Heart rate (beats/min)
- Respiratory rate (breaths/min)

The “Low”, “Normal” and “High” ranges for each vital signs (except heart rate) will be derived as described in [Table 13](#):

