### 3 STUDY ENDPOINTS

#### 3.1 Primary Endpoints

Safety variables include AEs, clinical laboratory variables, vital signs and suicidal behavior.

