**Table 13 Low, Normal and High Ranges for Vital Signs (Temperature, SBP, DBP and Respiratory Rate)**

Parameters	Range		
	Low	Normal	High
Temperature (°C)	< 35.8	35.8 -37.5	> 37.5
SBP (mmHg)	< 90	90 -150	>150
DBP (mmHg)	< 45	45 – 90	> 90
Respiratory rate	< 12	12 – 25	> 25

Actual value and change from baseline will be summarized for each parameter and visit by treatment group and overall using descriptive statistics in the SAF set on DBTP period.

Treatment-emergent out-of-range values are defined as follows:

- with normal values at baseline and low or high value at any post baseline visit, or
- with low values at baseline and high at any post baseline visit, or
- with high values at baseline and low at any post baseline visit.

If baseline is missing any postbaseline abnormality will be considered treatment-emergent.

Shift tables will be created to summarize the number and proportion of participants with shifts from baseline to all visits according to the normal range “Low”, “Normal”, “High” and “Treatment-emergent” by treatment group and visit. The worst post DBTP baseline will also be presented. In case of low and high post- baseline values, a category ‘low + high’ will be defined. Numbers of participants with treatment-emergent abnormalities will also be shown.

All vital signs data will be listed for participants with post- baseline abnormalities.

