#### 6.4.4 Electrocardiogram

Triplicate 12-lead ECGs are performed at screening and V1 visit and single 12-lead ECG for the other visits. For the other visits, a single 12-lead ECG is performed. Mean values of the triplicates will be calculated per time point and rounded to 1 decimal. Throughout the analysis, including the derivation of baseline and abnormalities, the mean values will be used in case the assessment was performed in triplicates. Individual triplicate values will only be listed.

ECG parameters include heart rate, PR, QRS, QT, QTcB and QTcF intervals.

The “Low”, “Normal” and “High” ranges will be derived for heart rate, PR and QRS as described in [Table 14](#).

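### Vital-sign heart rate has no Low/Normal/High range, so heart-rate abnormality is counted only on ECG: 2 of 13 scheduled post-baseline visits

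*SAP*

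**What the plan says.** Section 3.1 gives the primary endpoints: "Safety variables include AEs, clinical laboratory variables, vital signs and suicidal behavior". ECG is not named there, nor among the primary endpoints in Section 1.2.

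Section 6.4.3 lists temperature, systolic and diastolic blood pressure, heart rate and respiratory rate as vital signs. It then says that the Low, Normal and High "ranges for each vital signs (except heart rate) will be derived as described in" Table 13. The table's title names the four parameters that it covers: "Low, Normal and High Ranges for Vital Signs (Temperature, SBP, DBP and Respiratory Rate".

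The outputs in Section 6.4.3 are of three kinds:
- Descriptive: "Actual value and change from baseline will be summarized for each parameter and visit by treatment group and overall".
- Categorical: shift tables showing "shifts from baseline to all visits according to the normal range", the worst post-baseline category, and counts of treatment-emergent out-of-range values.
- A listing (16.2.8.2.1) of all vital-sign data, restricted to participants who have a post-baseline abnormality.

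In Section 6.4.4, on ECG, the corresponding "ranges will be derived for heart rate, PR and QRS as described in" Table 14. The heart-rate limits there are below 40, 40 to 100, and above 100 beats/min.

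**The concern.** Every categorical vital-sign output needs a Low, Normal or High label, and vital-sign heart rate never receives one. Section 6.2.1.3 creates a worst-case visit only for parameters with a defined abnormality or toxicity grade, so that route is closed too. The treatment-emergent definition in Section 6.4.3 compares post-baseline with baseline categories, which heart rate lacks.

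Heart rate is classified on ECG, but the ECG schedule is much sparser. A participant whose heart rate goes out of range between ECGs, with no other abnormal vital sign, is counted in no abnormality table and does not reach the vital-sign listing. The by-visit mean, quartiles, minimum and maximum show that an extreme value occurred. They do not show how many participants were out of range in each arm, or whether the finding was new since baseline. The SAP collects these readings for a primary safety endpoint and does not say why they are left unclassified.

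**Working it through.** The SAP states no figure to reproduce; the check is a count from Table 19.

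**1. Which column is which visit.** The visit header of Table 19 is not legible in the public copy. The pregnancy-test row is marked in columns 1, 6, 8, 11, 12 and 14, with a discretionary mark in column 16. Its footnote names V1, V6, V8, V11, V12, V14/ED and unscheduled visits. The two agree, so columns 1 to 14 are V1 to V14/ED and column 16 is the discretionary unscheduled visit. Column 15 is read as the unscheduled IVIg visit.

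**2. Visits with each assessment.**
- Vital signs: columns 1 to 15, plus discretionary. Scheduled post-baseline: V2 to V14/ED = 13.
- ECG: columns 1, 8 and 14, plus discretionary. Scheduled post-baseline: V8 and V14/ED = 2.
- Heart rate measured but not classified: 13 − 2 = 11 visits; 11/13 = 85%. Heart rate classified on ECG: 2/13 = 15%.
- V2 is optional (footnote to Table 21). Without it: 12 − 2 = 10; 10/12 = 83%.
- Column 15 has a mark for vital signs and none for ECG.

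**3. Unscheduled readings.** Section 5.5 keeps, per window, the value closest to the target day. For other parameters, Section 6.2.1.3 brings unscheduled readings back through the worst-case visit. For vital-sign heart rate it does not, so an out-of-range unscheduled reading that is not closest to target appears in no table, even as a minimum or maximum.

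**4. How much this could matter per participant.** The SAP gives no rate of out-of-range heart rate. Assume 5% per visit, and count any post-baseline out-of-range value whatever the baseline category.
- Independent visits: ECG visits 1 − 0.95² = 9.8%; all vital-sign visits 1 − 0.95¹³ = 48.7% (1 − 0.95¹² = 46.0% without V2).
- Full persistence (the same 5% of participants out of range at every visit): 5% on either schedule.
- Range: 5% to 9.8% on ECG visits against 5% to 48.7% on all visits.

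**5. The listing.** Four classified parameters at 13 visits give 52 readings. If each is abnormal with probability p, independently, the chance of qualifying through a parameter other than heart rate is 1 − (1 − p)⁵². This is 5% at p = 0.1%, 41% at p = 1% and 93% at p = 5%. These values of p are also assumed.

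**The case against.** The strongest reply is that this is a stated choice and not a slip. The exception is in the text, the title of Table 13 repeats it, and the next section classifies heart rate on the 12-lead ECG, with a triplicate mean at V1. Sections 6.4.3 and 6.4.4 do not contradict each other. An ECG prompted by an abnormal pulse could be taken at an unscheduled visit, and it would enter the worst post-baseline derivation. The trial is exploratory, with 16 planned per arm and no formal testing. All of that stands. It does not supply a reason for leaving the more frequent readings unclassified, and ECGs at V8 and V14/ED can miss a change that comes and goes between them.

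Three stronger readings are tempting, and the SAP does not support them:
- **Heart-rate data are discarded.** They are not. Values and changes are summarized at each visit, subject to the rule in Section 6.2.1 that a visit needs at least 15 participants to be shown.
- **Most heart-rate readings never reach the listing.** This cannot be shown. The listing selects participants, not readings, and prints all vital signs for anyone selected. The 5% to 93% range above shows how far the answer depends on an assumed rate. What holds is that heart rate alone cannot trigger it.
- **Detection falls from 48.7% to 9.8%.** That contrast needs independent visits. Out-of-range heart rates tend to recur in the same people, which narrows the gap, to nothing under full persistence.

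**Conclusion.** The point holds in limited form. As written, one of five vital signs in a primary safety endpoint has no abnormality count of its own, and heart-rate abnormality is assessed categorically at 2 of 13 scheduled post-baseline visits in the double-blind period. That count rests on the column mapping of Table 19, which the pregnancy-test footnote supports. The effect on the chance of flagging a participant runs from none to roughly fivefold (48.7/9.8) at an assumed 5% per-visit rate, depending on how strongly visits are correlated. No primary conclusion is shown to change. This is an inexpensive improvement worth making, not a fault that undermines the safety analysis.

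**What to change.** In Section 6.4.3, remove the exception for heart rate and add a heart-rate row to Table 13, with an analysis range set by the sponsor. The Table 14 limits, already used for ECG heart rate, are one option; the SAP does not say that they apply to vital-sign readings, so the choice should be stated. Amend the title of Table 13 to match. Vital-sign heart rate then enters the shift, worst post-baseline and treatment-emergent outputs, and can trigger Listing 16.2.8.2.1. Scheduled post-baseline visits with a classified heart rate rise from 2 to 13.

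The cost is one row in the SAP and in existing programs, a few extra rows in the outputs, and some incidental out-of-range flags to interpret. No new data are needed. If the sponsor prefers to keep the exception, Section 6.4.3 should say why ECG heart rate is sufficient; that documents the choice but does not supply the missing counts.

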**Table 13 Low, Normal and High Ranges for Vital Signs (Temperature, SBP, DBP and Respiratory Rate)**

Parameters	Range		
	Low	Normal	High
Temperature (°C)	< 35.8	35.8 -37.5	> 37.5
SBP (mmHg)	< 90	90 -150	>150
DBP (mmHg)	< 45	45 – 90	> 90
Respiratory rate	< 12	12 – 25	> 25

Actual value and change from baseline will be summarized for each parameter and visit by treatment group and overall using descriptive statistics in the SAF set on DBTP period.

Treatment-emergent out-of-range values are defined as follows:

- with normal values at baseline and low or high value at any post baseline visit, or
- with low values at baseline and high at any post baseline visit, or
- with high values at baseline and low at any post baseline visit.

If baseline is missing any postbaseline abnormality will be considered treatment-emergent.

Shift tables will be created to summarize the number and proportion of participants with shifts from baseline to all visits according to the normal range “Low”, “Normal”, “High” and “Treatment-emergent” by treatment group and visit. The worst post DBTP baseline will also be presented. In case of low and high post- baseline values, a category ‘low + high’ will be defined. Numbers of participants with treatment-emergent abnormalities will also be shown.

All vital signs data will be listed for participants with post- baseline abnormalities.

#### 6.4.4 Electrocardiogram

Triplicate 12-lead ECGs are performed at screening and V1 visit and single 12-lead ECG for the other visits. For the other visits, a single 12-lead ECG is performed. Mean values of the triplicates will be calculated per time point and rounded to 1 decimal. Throughout the analysis, including the derivation of baseline and abnormalities, the mean values will be used in case the assessment was performed in triplicates. Individual triplicate values will only be listed.

ECG parameters include heart rate, PR, QRS, QT, QTcB and QTcF intervals.

The “Low”, “Normal” and “High” ranges will be derived for heart rate, PR and QRS as described in [Table 14](#).

**Table 14 Low, Normal and High Ranges for ECG parameters (Heart rate, PR and QRS)**

Parameters	Range		
	Low	Normal	High
Heart rate (beats/min)	< 40	40 -100	> 100
PR (ms)	< 120	120 – 220	> 220
QRS (ms)	< NA	0-120	> 120

NA: Not Applicable

Treatment-emergent out-of-range values are defined as follows :

- with normal values at baseline and low or high value at any post baseline visit, or
- with low values at baseline and high at any post baseline visit, or
- with high values at baseline and low at any post baseline visit.

If baseline is missing any postbaseline abnormality will be considered treatment-emergent.

For QTcB and QTcF (ms), the following categories will be derived:

- For the actual values: ≤ 450 (normal), ]450 ;480], ]480 ; 500], and > 500
- For the change from baseline: ≤ 30 (normal), ]30;60] and > 60.

For QTcB and QTcF, a treatment-emergent abnormality is defined as any postbaseline abnormality which was not present at baseline or which worsened following baseline (eg, QTcF ]450; 480] ms at baseline and >500 ms postbaseline). If baseline is missing any postbaseline abnormality will be considered treatment-emergent.

ECG parameters (heart rate, PR, QRS, QT, QTcB and QTcF intervals) will be summarized using actual value and change from baseline at each visit/time point by treatment group and overall in the SAF set on the DBTP.

For heart rate, PR and QRS, shift tables will also be created to summarize the number and proportion of participants with shifts from baseline category to “Low”, “Normal”, “High”, treatment-emergent by treatment group and visit . Shift tables from baseline to worst post DBTP baseline category will also be presented. In case of low and high post- baseline values, a category ‘low + high’ will be defined.

All ECG data for participants with post baseline abnormalities will be listed.

For QTc, shift tables will be created to summarize the number and proportion of participants with shifts from baseline to all visits according to the abnormality by treatment group and visit. Shift tables from baseline to worst post DBTP baseline abnormality will also be presented. Numbers and cumulative numbers of participants with treatment-emergent abnormalities will also be shown.

Abnormalities of QTc changes will be summarized at each post-baseline analysis visit and at the worst-post-Baseline analysis visit. Number and Cumulative numbers of participants with change abnormalities will also be shown.

#### 6.4.5 Suicidal Behavior

All suicidal behavior evaluations will be performed in SAF set.

Suicidality assessments are conducted by specifically answering the following question, derived from the Patient Health Questionnaire (PHQ-9) depression questionnaire:

“Over the last 2 weeks, how often have you been bothered by thoughts that you would be better off dead, or of hurting yourself in some way?”

Possible answers with the associated scores are:

- “Not at all [0]”,
- “Several days [1]”,
- “More than half the days [2]”,
- “Nearly every day [3]”.

Number and percentage of participants for each answer will be summarized at each visit during DBTP in the SAF set. The worst DBTP post baseline suicidal ideation during DBTP will also be reported.

All PHQ-9 assessments will be listed, but only for participants with a post baseline PHQ-9 answer not equal to ‘Not at all’.

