### **Double-Blinded Treatment Period (DTBP)**

For each cohort:

The dosing of IMP will begin at V1 and continue throughout the DBTP.

[figure not shown]
- The DBTP will begin 7 days after the final IVIg administration of the IVMP

- Participants will be randomized at day 1 of the DBTP (Figure 1):
  - [REDACTED]
  - [REDACTED]
  - [REDACTED]
  - [REDACTED]
  - Randomization will be stratified based on an individual's IVIg dose frequency as described in Section 2.2.
- For cohort 2, the dose regimen chosen by the EDRT will remain blinded to the participant, investigator, and the sponsor's study team to avoid any bias in the outcome assessments.
- Participants will be treated with IVIg during the DBTP if there is a clinically meaningful deterioration in muscle strength and/or motor function. [REDACTED]  
[REDACTED]  
[REDACTED]
  - Administration of IMP will not be paused/stopped when IVIg retreatment is initiated
  - Based on their clinical judgment, the investigator may choose to not re-treat the participant with IVIg in the event of a clinically meaningful deterioration
  - All study participants can request IVIg retreatment with the investigator anytime during the DBTP.

The following interim database locks will occur:

- After the completion of the 16-week DBTP by all participants included in cohort 1. Only participants from cohort 1 will be unblinded
- After the completion of the 16-week DBTP by the 24th participant included in cohort 2. The second interim analysis will include all participants included in cohort 2 and all participants of cohort 2 will be unblinded, even ongoing participants.

A final database lock will occur when all participants have completed the safety follow-up period, or have rolled over to the long-term extension (LTE) study, if applicable.

[figure not shown]

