**EQ-5D-5L**

These analyses will be performed in SAF set.

The EuroQol 5-dimension questionnaire (EQ-5D-5L) consists of 2 parts:

- A descriptive system of 5 dimensions: mobility, self-care, usual activities, pain/discomfort and anxiety/depression. Each dimension has 5 levels of response ranging from 1 (no problem) to 5 (extreme, unable to do so)
- A 20-cm vertical visual analog scale (VAS) with endpoints 0 (the worst health you can imagine) and 100 (the best health you can imagine).

For the last assessment analysis visit during DBTP and last assessment before first IVIg retreatment analysis visits, categories of improvement will be classified as follow:

- No change: the score is equal to baseline
- Improved: the score is lower than baseline
- Worsened: the score is higher than baseline

On IVMP, the number and percentage of participants will also be summarized by level at each visit for each dimension. Actual value and change from IVMP baseline in the VAS Score will be summarized on IVMP.

On DBTP, for each dimension, the number and percentage of participants will be summarized by level at each visit (as defined in [6.2.1.2](#)). The percentage of Improvement/worsening/no change will be also displayed for the last analysis visits.

Shift tables will be created to summarize the number and proportion of participants with shifts from baseline levels to last assessment derived visit (as defined in [6.2.1.2](#)) for each dimension by treatment group and overall.

Actual value and change from baseline in the VAS Score will be summarized on DBTP.

EQ-5D-5L data will be listed.

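### PHQ-9 item 9 is tabulated without reference to each participant's baseline, so the planned table gives no by-arm count of new or worsened ideation if anyone scores above 0 at baseline

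*SAP*

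**What the plan says.** SAP 1.2 and 3.1 list suicidal behavior among the primary safety variables, and the primary objective is a comparison with placebo. After screening it is monitored by one PHQ-9 question, scored 0 to 3, which begins "Over the last 2 weeks, how often have you been bothered by thoughts".

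Section 6.4.5 plans three outputs:

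- By visit: "Number and percentage of participants for each answer will be summarized at each visit during DBTP in the SAF set".
- Worst case: "The worst DBTP post baseline suicidal ideation during DBTP will also be reported".
- A listing: "All PHQ-9 assessments will be listed, but only for participants with a post baseline PHQ-9 answer not equal to" the lowest answer.

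Table 24 contains one suicidality table, 14.3.4.4.1, marked for interim analysis 2 and the final analysis. Its title names participants with ideation during the DBTP and mentions no shift. Table 25 contains one suicidality listing, 16.2.8.4.1, marked for interim analysis 1 and the final analysis.

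A baseline answer is available. The schedule in 9.1 has item 9 at the IVIg monitoring visits and at V1, with V1 assessments done before IMP unless stated otherwise, and 6.2.3 defines the DBTP baseline.

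**The concern.** A participant who reports ideation on several days at baseline and stays there is counted in the same row as one who moves there from a score of 0 after starting IMP. For a safety comparison with placebo, the useful quantity is how many participants per arm became worse than they were before dosing. The planned table gives how many had ideation, whatever its origin.

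Elsewhere the SAP makes the link. Laboratory values (6.4.2) and vital signs (6.4.3) have shifts from baseline with a treatment-emergent rule. QTc (6.4.4) has a rule covering abnormalities that are new or have worsened. For ANA titers the plan has "Shift tables from baseline to worst post baseline category". EQ-5D-5L, also an ordinal self-report, has a table of "participants with shifts from baseline levels to last assessment derived visit". Item 9 has none of these, and no reason is given.

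**Working it through.** The SAP states no figure to reproduce here: 6.1 says no formal sample size calculation was made. The check is what the planned counts can and cannot determine.

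**Step 1. What the worst-answer rows combine.** Four baseline answers by four worst post-baseline answers give 4 × 4 = 16 cells. The table reports only the 4 worst-answer totals. The positive rows break down as follows:

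- Worst = 1: 1 cell worsened (baseline 0), 1 unchanged, 2 improved (baseline 2 or 3).
- Worst = 2: 2 worsened (baseline 0 or 1), 1 unchanged, 1 improved (baseline 3).
- Worst = 3: 3 worsened (baseline 0, 1 or 2), 1 unchanged.

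The three positive rows therefore pool 6 + 3 + 3 = 12 cells: 6 new or worsened, 3 unchanged, 3 improved.

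**Step 2. Would showing baseline totals by arm be enough?** Not in general. The table below takes n = 16 (the per-arm number in 6.1) and assumed totals for answers 0/1/2/3. It bounds the number with worst answer above baseline answer over every cross-table consistent with both sets of totals.

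| Baseline totals | Worst totals | New or worsened |
|---|---|---|
| 14/2/0/0 | 14/2/0/0 | 0 to 2 |
| 13/3/0/0 | 12/3/1/0 | 1 to 4 |
| 14/1/1/0 | 13/2/1/0 | 1 to 3 |
| 16/0/0/0 | 14/2/0/0 | exactly 2 |

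The last line shows the exception: with nobody positive at baseline, the worst-answer rows are already the new cases.

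**Step 3. Size of the ambiguity.** Let k participants score 1 at baseline and k score 1 as worst answer, all others 0, with n at least 2k. New cases = k − overlap, and overlap can be 0 to k, so new cases run from 0 to k. Column sizes under 2:1 randomization of 24 per cohort: cohort placebo 24 × 1/3 = 8; cohort 1 active 24 × 2/3 = 16; pooled placebo 8 + 8 = 16.

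- k = 0: no ambiguity.
- k = 1: up to 1/8 = 12.5 or 1/16 = 6.3 percentage points.
- k = 2: up to 2/8 = 25.0 or 2/16 = 12.5 percentage points.

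The value of k is assumed; the SAP gives no baseline prevalence.

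**Step 4. Which analyses have the listing.** Anyone new or worsened has a non-zero post-baseline answer, so the listing includes every such participant with all their assessments.

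- Interim analysis 1, timed "After the completion of the 16-week DBTP by all participants included in cohort 1": listing marked, so cohort 1 can be resolved.
- Interim analysis 2: "The second interim analysis will include all participants included in cohort 2 and all participants of cohort 2 will be unblinded, even ongoing participants". Table 14.3.4.4.1 is marked, but the listing is not. This is a general choice: of the 50 listings legible in Table 25, only the pharmacodynamic one (16.2.6.3.1) is marked for this analysis.
- Final analysis: table and listing are both marked, so every case can be resolved.

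**The case against.** The strongest reply is that the listing already captures every participant who could be new or worse, alongside their earlier answers. With 48 participants planned in an exploratory trial without formal testing, a hand count is short work. That stands, and it limits the point to presentation and timing. A reader might infer from 6.4.5 that new ideation cannot be identified at all. The documents do not support that: it can be identified for everyone at the final analysis and for cohort 1 from interim analysis 1.

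It can also be said that cohort 2 at interim analysis 2 is not wholly unobserved. The TEAE tables, restricted to onset on or after first IMP, are marked for that analysis and would show new ideation reported as an adverse event. The IDMC also receives its own unblinded safety reports (2.4). Both are true. However, adverse event tables depend on investigator reporting and are not an item-9 count, and the SAP does not say whether the IDMC reports link item 9 to baseline.

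A third reply is that baseline ideation may be absent. The C-SSRS is used at screening, but whether it excluded anyone is not stated in the SAP. If nobody is positive at baseline, the concern disappears; the plan cannot count on that in advance.

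Finally, shifts for laboratory values, vital signs and ECG rest on defined ranges or grades, and EQ-5D-5L is an efficacy instrument, so they set no rule for item 9. That is fair. They show only that the link is feasible and is the SAP's usual practice.

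**Conclusion.** The point holds as a minor, nearly free improvement. As written, 6.4.5 and Table 14.3.4.4.1 give unlinked totals, and if any participant scores above 0 at baseline these do not in general yield the number per arm with new or worsened ideation. The practical gap is a missing by-arm count and, for cohort 2 at interim analysis 2, the lack of any item-9 output tied to baseline.

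A reader might go further and conclude that the table can never give the count. That is not so: with nobody positive at baseline, the worst-answer rows give it exactly. The percentage-point ranges depend on the assumed k and illustrate the ambiguity; they do not predict what this trial will show. The conclusion also takes Table 24's title and the text of 6.4.5 as describing the table in full, since its layout is not in the SAP.

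**What to change.** In 6.4.5, define new or worsened ideation as a DBTP post-baseline item-9 score above the DBTP baseline score, or any post-baseline score of 1 or more if baseline is missing. The missing-baseline rule matches the one already used for laboratory values, vital signs and ECG. Add to Table 14.3.4.4.1 a shift from baseline to worst DBTP post-baseline answer, with the new-or-worsened count by treatment group. The table is already marked for interim analysis 2 and the final analysis, so the cohort 2 gap closes without changing any listing.

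Optionally, footnote the two-week recall. An answer at the optional Day 4 visit covers about 11 pre-dose days out of 14 (11/14 = 79%), and only from Day 15 is the recall window wholly post-dose.

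The cost is a sentence or two of SAP text and one 4 × 4 panel per treatment group on data already collected. The panel will be sparse, with many cells possibly empty, but the count line stays readable at these arm sizes. Sample size and assessments do not change.
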